7.5.1.5 Prior to Discharge

The investigator will remove the electrodes prior to ICU discharge or 30 days post-implant procedure, whichever comes first. The electrodes may be withdrawn earlier if the patient has been successfully extubated (and will no longer be at risk of re-intubation). After removal, subjects will be monitored for adverse events prior to ICU discharge or 30 days post-implant procedure, whichever comes first.

7.5.1.6 30 Days Post Electrode Removal

For implanted patients a follow-up questionnaire will be administered by phone, email, or visit to assess at 30 days post-electrode removal the subject's survival, any readmission or reintubation, any post-procedure complications, and subject's location (home, nursing home, long term acute care hospital).

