7.5 Procedures

7.5.1 Description of Investigational Procedures

Table 2 lists the data to be collected at each study interval. Study activities are recorded on the case report forms by the clinical coordinator or other clinician designated by the principal investigator. The clinician completing the form signs in the entry designated for completion and the principal investigator reviews all forms and signs in the designated location to indicate review and confirmation of the data entered.

Table 2a: Schedule of Study Activities and Data Collection – Initial All Patients

Activity/Procedure/ Assessment	Screening and Enrollment	At Time of Cardiac Surgery	ICU
Informed Consent	X		
Inclusion/non-inclusion criteria	X		
Demographics, medical history	X		
TransLoc electrode insertion		X	
Concomitant Interventions		X	
Serious adverse events		X	
Adverse device effects		X	

Activity/Procedure/ Assessment	Screening and Enrollment	At Time of Cardiac Surgery	ICU
Device deficiencies		X	
Randomization		X	
Concomitant Interventions			X
Start / Stop date and time of MV use			X
EMG Baseline recording			X

Table 2b: Schedule of Study Activities and Data Collection – Treatment Patients

Activity/Procedure/ Assessment	ICU
Start / Stop date of TransAeris stimulation	X
Competing events	X
Serious adverse events	X
Adverse device effects	X
Device deficiencies	X

Table 2c: Schedule of Study Activities and Data Collection – Control Patients

Activity/Procedure/ Assessment	ICU First 120hrs	ICU At 120hrs	ICU After 120hrs
EMG VIDD Progression recording		X	
TransAeris Start & Settings		X	
TransAeris Start/Stop & Settings			X
Competing events	X	X	X
Serious adverse events	X	X	X
Adverse device effects	X	X	X
Device deficiencies	X	X	X

Table 2d: Schedule of Study Activities and Data Collection – Conclusion All Patients

Activity/Procedure/ Assessment	Discharge	30 Days Post Electrode Removal
Serious adverse events	X	X
Adverse device effects	X	
Device deficiencies	X	
EMG Wean/Discharge recording	X	
TransLoc electrode removal	X	
Follow-up questionnaire		X

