15.3.1 Investigator reporting Responsibilities

Investigators must report to the sponsor, without delay (immediately) and not later than 3 calendar days after his awareness, all adverse device effects (ADEs), device deficiencies and serious adverse events (SAEs) study subjects experience during participation in this investigation.

Each reported event must be appropriately documented to include the event's serious criterion, relatedness, treatment, and resolution. All reported events that remain unresolved should be re-assessed until the event resolves or the subject's study participation is complete. In the event of subject death, the investigator will make reasonable effort to obtain a death summary, autopsy report, etc.

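### Non-serious device effects after discharge have no scheduled, device-specific collection, so device-related adverse events can be under-counted

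*Combined protocol and SAP*

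**What the plan says.** Section 7.5.1.5 sets the time of removal: "The investigator will remove the electrodes prior to ICU discharge or 30 days post-implant procedure, whichever comes first". Removal before that limit is allowed: "The electrodes may be withdrawn earlier if the patient has been successfully extubated". The same paragraph then closes post-removal monitoring: "After removal, subjects will be monitored for adverse events prior to ICU discharge or 30 days post-implant procedure, whichever comes first".

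The schedule for the end of the study is in "Table 2d: Schedule of Study Activities and Data Collection – Conclusion All Patients". It has two columns, Discharge and "30 Days Post Electrode Removal". Serious adverse events are ticked in both. Adverse device effects and device deficiencies are ticked at Discharge only. The follow-up questionnaire is ticked at 30 days. Section 7.5.1.6 says that it covers survival, the subject's location, and "any readmission or reintubation, any post-procedure complications". No item on device effects or the exit site is named.

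Section 15.3.1 obliges investigators to report "all adverse device effects (ADEs), device deficiencies and serious adverse events (SAEs) study subjects experience during participation in this investigation". The synopsis counts a 30-day follow-up after explant as part of each subject's time in the study. Section 7.5.1.7 lists ADEs among the things each subject is monitored for and gives no end date.

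**The concern.** The plan does not give one answer to the question of when ADE collection ends. It could be the limit in 7.5.1.5, the Discharge column of Table 2d, or the end of participation under 15.3.1. A site that follows the first two will not ask about device effects after discharge, even though it speaks to the subject 30 days after removal.

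This matters because section 7.2.3 names device-related adverse events as an ancillary safety outcome, with no restriction to serious ones. Section 5.2 lists bleeding and exit-site pain after removal among the procedure risks, and exit-site infection needing antibiotics among the device risks. These can be non-serious, so the serious-event tick at 30 days need not pick them up. Every subject is implanted, including controls who are never stimulated, so the gap applies to both arms.

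An event that is not elicited leaves no trace later. Section 8.2 counts subjects with a recorded event, section 8.7 imputes nothing, and under section 16 the Medical Monitor reviews the ADEs that the site has reported. Identifying safety concerns, and testing whether the evaluation criteria can be collected, are both stated objectives (section 6.2).

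**Working it through.** There is no stated figure to reproduce. The check sets the passages side by side and then works out the length of the gap.

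**Step 1. What each place covers after removal**

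| Place | What is collected | Until when |
|---|---|---|
| 7.5.1.5 | Adverse events | ICU discharge or day 30 post-implant, whichever is first |
| Table 2d | ADEs, device deficiencies | Discharge (ICU or hospital not stated) |
| Table 2d | Serious adverse events | 30 days after removal |
| 7.5.1.6 | Questionnaire with a general complications item | 30 days after removal |
| 15.3.1 with the synopsis | ADEs, deficiencies, serious adverse events | End of participation, 30 days post-explant |

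Serious device effects are covered to 30 days by rows 3 and 5. Non-serious device effects after discharge are covered only by the general item in row 4 and the reporting duty in row 5. Neither is a scheduled assessment of device effects.

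**Step 2. Length of the window under 7.5.1.5**

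Let k be the number of days by which removal precedes the limit. Monitored days after removal = k. Days left to the 30-day contact = 30 − k.

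- k = 0: 0 days monitored, 30 left
- k = 2: 2 monitored, 28 left
- k = 5: 5 monitored, 25 left
- k = 10: 10 monitored, 20 left

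The documents do not give the distribution of k. If Discharge in Table 2d means hospital discharge, scheduled ADE collection runs on from the ICU to that day, and the gap is shorter by the length of the ward stay, which is also not given.

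**Step 3. Does the pilot show that such effects are negligible?**

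Section 5.2 reports 0 of 32 for bleeding after removal and 0 of 32 for exit-site pain after removal. Exact upper limits for each:

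- one-sided 95%: 1 − 0.05^(1/32) = 8.9%
- upper end of the two-sided 95% interval: 1 − 0.025^(1/32) = 10.9%

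So the pilot does not rule out a true rate near one in ten for either effect.

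**Step 4. How many would be missed?**

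This needs the rate of non-serious device effects after discharge and the share that the general item or a spontaneous report would catch. The documents give neither, so no figure follows.

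**The case against.** The strongest case against the point is that the plan already has several routes to these events. The 30-day contact exists. Its complications item could bring out pain, bleeding or infection. The reporting duty in 15.3.1 does not lapse at discharge. A duty to report and a schedule of planned assessments can stand together, so the passages are not strictly incompatible. The outcome affected is ancillary and descriptive.

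Most of this stands, and it narrows the point. It does not close it: a general question asked 30 days later is a weaker instrument than a device-specific one, and the schedule tells the site that ADEs are not due at that contact.

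Three further objections stand in full:

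- **Zero days is a worst case.** It applies only when electrodes come out at the limit. Removal after successful extubation leaves some monitored time.
- **Retained fragments are a poor example.** Section 3.6.3 has each wire examined at removal and any fragment documented. For the same reason, little would be gained by also ticking device deficiencies at 30 days, when the device is out.
- **An illustration with an assumed rate proves little.** A reader might assume that 5% to 10% of subjects have such an effect, expect 30 × 0.05 = 1.5 to 30 × 0.10 = 3 events, suppose that all are missed, and conclude that the trial would report 0 of 30 with a falsely low upper limit. That limit is 1 − 0.025^(1/30) = 11.6%, which still covers the whole assumed range. The rate is not in the documents, and missing every event is a ceiling, not an expectation.

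**Conclusion.** The point holds for non-serious device effects after discharge. They have no scheduled, device-specific collection, and 7.5.1.5 and Table 2d stop short of the reporting period implied by 15.3.1 and the synopsis. The ancillary count of device-related adverse events can be too low as a result.

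A reader might infer that all adverse event monitoring stops at ICU discharge or day 30, or that the primary safety endpoint is at risk. The documents support neither. Serious adverse events are scheduled at 30 days after removal. The primary endpoint is serious adverse device effects (8.4.1), which are by definition a subset of those events and would be classified for causality under 15.2.

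The size in time is up to 30 days per subject, less whatever interval lies between removal and the limit or Discharge. The size in events cannot be computed. The conclusion assumes that the site works to the written schedule and that the questionnaire contains no device-specific items beyond those described in 7.5.1.6; the questionnaire itself is not in the documents. This is an inexpensive improvement to safety data collection, not a threat to the main result.

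**What to change.** - Align 7.5.1.5, Table 2d and 15.3.1 so that ADE collection runs to the contact 30 days after electrode removal for every implanted subject in both arms.
- Tick adverse device effects in the 30-day column of Table 2d.
- Add items on exit-site pain, bleeding and infection to the existing questionnaire.
- State whether Discharge in Table 2d means ICU or hospital discharge.
- Reconcile the removal-timing statements: 7.5.1.5 refers to ICU discharge, 3.6.3 to hospital discharge. Which is intended is for the sponsor and investigators to settle.

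The cost is a few questions at a contact that already takes place, with no new visit. The reported ADE rate may rise slightly because events are being asked about.

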3.6 Description of Investigational Device

3.6.1 *Introduction*

See User Manuals REF 77-1000-FR_B & REF 77-1002-FR_C for complete device instructions.

The TransAeris System is a temporary percutaneous intramuscular diaphragm stimulator intended for patients at risk of or on prolonged positive pressure mechanical ventilation (MV). TransAeris is indicated for use in the prevention and treatment of ventilator-induced diaphragm dysfunction (VIDD).

The TransAeris System includes four TransLoc® intramuscular diaphragm electrodes, the TransAeris external stimulator, and the FrictionLoc® connectors which provide the interface between the TransLoc electrodes and the TransAeris stimulator. Placement of the diaphragm electrodes can be performed in conjunction with another surgical procedure or as the primary procedure. TransAeris is used to provide neuromuscular electrical stimulation to the diaphragm while the patient is on mechanical ventilation to prevent, slow, or reverse diaphragm disuse atrophy and, more generally, to treat VIDD. Once the patient is successfully liberated from mechanical ventilation for 48 hours, the electrodes can be removed from the patient.

A cornerstone of the rationale and evidence supporting the use of intramuscular diaphragm stimulation in the treatment of VIDD comes from the clinical experience with Synapse's NeuRx DPS® (IDE (investigational device exemption) G920162, HDE (humanitarian device exemption) H070003). Patients who have been ventilator dependent for months to years due to chronic high-level spinal cord injury (SCI) have undergone a regimen of diaphragm stimulation with the permanently implanted NeuRx DPS to reverse disuse atrophy and re-educate the muscle. Although diaphragm dysfunction was advanced having accrued over months to years, diaphragm function was substantially restored after just a few days of reconditioning with intramuscular diaphragm stimulation.

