7.5.1.3.1 Treatment (Tx) Group

TransAeris use begins, in the Tx group as soon as practical. TransAeris stimulation will not begin unless the patient is connected to cardiac monitoring. The cardiac rhythm will be observed for any potential cardiac capture when stimulation is initiated, or any changes are made. The observation of cardiac rhythm interaction is recorded with the stimulator settings on the daily post-op case report form, page 5. TransAeris stimulator settings (stimulus intensity, stimulus frequency, and burst on/off) will be programmed to optimize diaphragm recruitment without compromising patient comfort. Refer to section 3.6.4.2 Device Programming. If stimulation settings cannot be adjusted or the stimulation cannot be applied without eliciting patient discomfort or pain due to the stimulation, then an adverse event indicated on the daily post-op case report form and an adverse event case report form, page 11, should be completed. Stimulation pain should be assessed daily using verbal and/or non-verbal cues from the patient using the visual analog scale shown below. In the event of pain that cannot be eliminated by reducing stimulation intensity then it should be recorded as such on the adverse event case report form.

TransAeris stimulation will continue as needed until the patient is successfully weaned. Stimulation may continue beyond successful weaning at the clinician's discretion to provide any additional support to avoid reintubation, but no longer than 30-days post-op.

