7.5.1.7 Adverse Events and Device Deficiencies

Each subject will be monitored for:

- Serious adverse events
- Adverse device effects
- Device deficiencies (malfunctions, failures, or technical issues)

The investigator and sponsor will assess the incidence of adverse events comparatively between the treatment and control patients. If a significant difference is identified, further study implants will be paused until resolution is identified.

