8.4.3 Secondary Endpoints

Secondary endpoints are defined as follows:

- All-cause mortality through 30 days
- Mechanical Ventilation time, as the cumulative time on mechanical ventilation from ICU entry and paralytic reversal to successful wean,
- Ventilator-free days, defined(15) as time free from mechanical ventilation during first 28 days, where:
$$\begin{aligned} VFD28 &= (28 - \text{Time on MV}) \text{ if Time on MV is less than 28 days;} \\ &= 0 \text{ if Time on MV} \geq 28 \text{ days} \\ &= 0 \text{ if death within 28 days} \end{aligned}$$
- Hospital length of stay (admission to discharge)
- ICU length of stay
- Change in median frequency and total power of the power density spectrum (PSD) analysis of inspirations at baseline, pre-stimulation, and post-stimulation in cross-over control patients

All endpoints will be summarized and reported descriptively to characterize outcomes. No *a priori* hypothesis testing is planned for this study.

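### Adverse events are compared between arms with no common observation window, because collection ends at points that depend on electrode removal, weaning and ICU discharge

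*Combined protocol and SAP*

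**What the plan says.** - **Last contact.** Section 7.5.1.6: "a follow-up questionnaire will be administered by phone, email, or visit to assess at 30 days post-electrode removal". It covers survival, readmission, reintubation and complications. Table 2d lists SAEs at discharge and again at this contact, and adverse device effects at discharge only.
- **When electrodes come out.** Section 7.5.1.5: "The investigator will remove the electrodes prior to ICU discharge or 30 days post-implant procedure, whichever comes first". It adds: "The electrodes may be withdrawn earlier if the patient has been successfully extubated".
- **When monitoring ends.** The same section: "After removal, subjects will be monitored for adverse events prior to ICU discharge or 30 days post-implant procedure, whichever comes first". This is not the end-point in Table 2d.
- **Stimulation.** Section 7.5.1.3.1: "Stimulation may continue beyond successful weaning at" the clinician's discretion, up to 30 days post-op. Under 7.5.1.3.2, controls are not stimulated unless they are still ventilated at 120 hours.
- **Comparison of arms.** Under 7.5.1.7 the investigator and sponsor will "assess the incidence of adverse events comparatively between the treatment and control patients", and a significant difference pauses further implants. No window, time origin or exposure adjustment is given.
- **Analysis.** Section 8.2 bases the primary adverse-event summary on subjects with the event. Section 8.3 uses all available data from all enrolled subjects, descriptively.
- **Mortality.** Section 8.4.3 lists "All-cause mortality through 30 days" without an origin. The same list gives one for ventilation time (ICU entry and paralytic reversal) and for hospital stay (admission).

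**The concern.** A subject count compares fairly between arms only if subjects are observed for the same time, or if the analysis allows for the difference. Here the clock stops at electrode removal plus 30 days, or at ICU discharge or day 30, depending on which section is followed. Each is reached after randomisation and each can be moved by treatment. If stimulation speeds weaning, treated patients lose their electrodes sooner and are observed for less time. If clinicians keep stimulating after weaning, treated patients keep their electrodes longer and are observed for more. Either way, an arm can show more events with no difference in risk.

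Two things are at stake: the between-arm safety comparison with its pause rule, and the event rates handed to the pivotal trial that 8.1 says this study will inform. A patient who dies with electrodes in place also has no removal date from which the last contact could be timed.

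**Working it through.** **1. The protocol's own figure.** Day of last contact = removal day + 30. The synopsis gives 1 to 30 days on device, and 7.5.1.5 caps removal at day 30.

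| Removal day | Last contact |
|---|---|
| 1 | POD 31 |
| 5 | POD 35 |
| 10 | POD 40 |
| 30 | POD 60 |

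The last row reproduces the synopsis figure of up to 60 days. The range is 60 − 31 = 29 days, or 60/31 = 1.94-fold. This contrasts extreme patients, not arms.

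**2. Expected gap between arms.** No distribution of removal days is given, so I assume removal follows weaning and use the planning figures:
- Still ventilated at 48 h among patients with prolonged ventilation (PMV): 65.9% control, 45.9% treated (4.2).
- Still ventilated at 120 h in controls: 34.8% (Table 1 total).
- PMV share of enrolled patients: 56.5% (4.2). Section 4.2 takes weaning before 24 h to be equal in both arms.
- Treated at 120 h (assumed): 30%, the complement of the 70% weaned in the pilot (4.1), or 0.348 × 0.459/0.659 = 24.2%.
- Still ventilated at day 30 (assumed): 0, or 10% of controls with the treated value scaled by the 120-h ratio.

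Among all enrolled patients, 0.565 × 0.659 = 37.2% of controls and 0.565 × 0.459 = 25.9% of treated patients are ventilated at 48 h, or 5.6 and 3.9 of 15.

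Mean days from day 1 to day 30 in PMV patients, with straight lines between points: A = 0.5(1 + S2) + 1.5(S2 + S5) + 12.5(S5 + S30).
- Control, S30 = 0: 0.83 + 1.51 + 4.35 = 6.69.
- Treated, S5 = 0.30, S30 = 0: 0.73 + 1.14 + 3.75 = 5.62. The difference is 1.07 days in PMV patients, and × 0.565 = 0.61 over all patients.
- Treated, S5 = 0.242, S30 = 0: A = 4.81. The difference is 1.88 days, or 1.06 over all patients.
- With the 10% tail, the differences are 1.24 and 2.26 days, or 0.70 and 1.28 over all patients.

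On this route the control window is about 0.6 to 1.3 days longer. Stimulation continued after weaning pushes the other way, by an amount the documents do not give.

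**3. Effect on incidence when risk is equal.** Assume the same constant hazard in both arms, h = −ln(1 − p30)/30, with risk by day t = 1 − exp(−ht). The documents give no SAE rate, so p30 is assumed. Base window: 35 days.

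| Assumed 30-day risk | +1 day | +2 days | +5 days | 31 v 60 days |
|---|---|---|---|---|
| 10% | 0.3 | 0.6 | 1.5 | 8.7 |
| 20% | 0.6 | 1.1 | 2.8 | 15.4 |
| 40% | 0.9 | 1.8 | 4.5 | 23.0 |

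Entries are percentage points. Worked example at 20%: h = 0.2231/30 = 0.00744; the risk is 22.9% by day 35 and 24.1% by day 37, a difference of 1.1 before rounding. One patient in an arm of 15 is 1/15 = 6.7 points.

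**4. With a fixed window.** Surgery to POD 30 gives 30 days in both arms, so the window difference is 0. Since removal on day 1 or later puts the existing contact at POD 31 or later, it can supply POD-30 status for every implanted patient reached.

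**The case against.** The case against is substantial, and much of it stands.

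- **Survival.** A reader might infer that mortality is to be compared over unequal windows. The documents do not say so. It is a fixed 30-day endpoint, and nothing defines it from electrode removal. Only the origin is missing.
- **Capture of deaths.** A reader might take the removal-anchored contact as the only survival check. It is not. The post-op form is completed for each day in protocol (7.5.1.3), death is an SAE (15.1), and death before weaning is a dated competing event (7.5.1.4). Deaths with electrodes in place are therefore recorded; what is undefined is the window in which they are counted.
- **Removal timing.** Section 3.6.1 says: "Once the patient is successfully liberated from mechanical ventilation for 48 hours, the electrodes can be removed from the patient". A reader might infer that this cannot be met alongside removal before ICU discharge. The wording is permissive and sets no minimum time in place, so there is no contradiction.
- **Scope of the comparison.** Section 7.3 places the treatment-control comparison in the first 120 hours and compares later outcomes with literature. That weakens the concern but does not remove it: 7.5.1.7 carries no 120-hour limit, and Tables 2c and 2d collect SAEs beyond that point.
- **Dependence on arm.** No removal rule differs by arm. The dependence is indirect and could go either way.
- **Importance.** The study is descriptive, with 30 implanted patients and no a priori tests. Adverse device effects, on which the primary safety endpoint rests, are scheduled only to discharge, so the late contact is not its main source. A post-explant contact is also a legitimate safety check in a device study.

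**Conclusion.** The concern holds for adverse events. Their collection has two conflicting end-points, both set by events that treatment can affect, while the between-arm comparison and pause rule have no common window or exposure adjustment. For mortality, the only fault is the unstated origin.

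The likely bias is small: about 1 day between arms (0.6 to 1.3) if removal follows weaning at the planning rates with the assumed tails, and 0.3 to 1.1 percentage points for a 1 to 2 day gap at assumed risks of 10% to 20%. Both are well below the 6.7 points that one patient represents. The net direction is unknown because discretionary stimulation could offset or reverse the weaning effect. The incidence figures assume a constant hazard; a hazard that falls after surgery would make extra late days matter less. They also use the removal-anchored window. Under the shorter window of 7.5.1.5 the same gap would be a larger share of follow-up, and the protocol gives no ICU-stay figures to size it. The change should be made because the window is uncontrolled and cheap to fix, not because a large bias has been shown.

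**What to change.** - In 7.5.1.7 and 8.4.3, count 30-day mortality and the between-arm SAE, reintubation and readmission comparisons from one stated origin, surgery or ICU admission, to POD 30. Apply this to all implanted patients whatever the electrode status, including those who die with electrodes in place. For a pause-rule look during enrolment, count patients not yet at POD 30 up to the date of the look.
- Keep the contact 30 days after removal and record event dates on its questionnaire.
- Report events after POD 30 separately as post-explant safety, with follow-up time by arm.
- Reconcile 7.5.1.5 with Table 2d on when adverse-event and SAE collection ends.
- For randomised patients who are not implanted, report what the chart review in 7.4.4 provides and state that POD-30 status may be incomplete. The questionnaire covers implanted patients only.

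The cost is wording in these sections and date fields on one form. No contact is added for implanted patients.
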